5.3.2.2. Randomization Phase – MRD-Positive Subjects (Open-Label)

In the Randomization Phase, subjects who do not achieve confirmed MRD-negative response (MRD-positive) will be randomized to receive open label treatment of I+V vs ibrutinib alone (venetoclax discontinued). For subjects receiving I+V, venetoclax can be administered for up to approximately 2 years per treatment course, until PD or unacceptable toxicity, or until this arm's study closure, whichever is earlier. Subjects continuing on ibrutinib at time of study arm closure may be offered a separate extension study to continue ibrutinib. The randomization will be stratified by IGHV status.

Ibrutinib + Venetoclax

- Orally once daily ibrutinib 420 mg (3 capsules) continuously until disease progression or unacceptable toxicity

plus

- Orally once daily venetoclax 400 mg (four 100 mg tablets)

OR**Ibrutinib**

- Orally once daily ibrutinib 420 mg (3 capsules) continuously until disease progression or unacceptable toxicity

Reintroduction of Ibrutinib or Venetoclax (MRD Cohort)

Upon confirmed MRD-positive relapse in MRD-negative randomized subjects or confirmed disease progression by IWCLL criteria in any randomized subjects, ibrutinib and/or venetoclax may be reintroduced (Figure 2).

[figure not shown]
Subjects who are receiving placebo treatment, when MRD-positive relapse or disease progression are confirmed, may reintroduce oral daily ibrutinib until disease progression or unacceptable toxicity.

Subjects who are receiving oral daily ibrutinib, when MRD-positive relapse or disease progression are confirmed, may reintroduce oral daily venetoclax. Standard TLS risk assessment, venetoclax dose ramp up, and TLS management should be employed at venetoclax reintroduction.

For those subjects who were treated with reduced dose(s) of ibrutinib or venetoclax during the Pre-randomization or Randomization Treatment Phase, a dose adjustment at the initiation of the Reintroduction period may be required, with escalation to full dose as tolerated.

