7.1.1.9. Tumor Lysis Syndrome (TLS) Risk Assessment

At baseline and prior to initiating venetoclax in Cycle 4, all study subjects will be assessed for risk of developing TLS. Ongoing risk of TLS should be assessed at all ramp up visits. The risk of TLS is a continuum based on multiple factors, including comorbidities. Subjects with high tumor burden (eg, any lymph node with a diameter ≥ 5 cm or high absolute lymphocyte count (ALC) [ALC $\geq 25 \times 10^9/L$]) are at greater risk of TLS when initiating venetoclax. Reduced renal function (creatinine clearance [CrCl] < 80 mL/min) further increases the risk. The risk may decrease as tumor burden decreases with venetoclax treatment.

Tumor burden assessments, including radiographic evaluation (eg, CT scans) as well as blood chemistry (creatinine, uric acid, potassium, phosphorus, and calcium) assessments will be performed in all subjects prior to initiating venetoclax treatment.

Appropriate venetoclax dosing and management of subjects throughout their study treatment is guided by their individual risk for developing TLS. Risk-based TLS prophylaxis and management measures are described in [Section 5.4.2.2](#).

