8.2. MRD Cohort

For the MRD cohort, the study is divided into a Screening Phase, a Pre-randomization Treatment Phase, a Randomization Phase, and a Post-PD Follow-up Phase. The Schedule of Assessments ([Appendix A](#)) summarizes the frequency and timing of efficacy, PK, [REDACTED] and safety measurements applicable to this study. The timing of all visits will be based on using Cycle 1 Day 1 (C1D1) as the anchor visit and all subsequent visits should use the C1D1 date as the basis for scheduling.

MRD Cohort: Pre-Randomization Treatment Phase

Refer to the Schedule of Assessments ([Appendix A](#)) for a complete list of procedures to be performed at each scheduled study visit.

Following completion of the Screening Visit and once eligibility has been confirmed (per inclusion/exclusion criteria), subjects will initiate ibrutinib treatment. Venetoclax will be added to ibrutinib treatment and initiated after completion of 3 cycles of ibrutinib. The venetoclax dose will be ramped up over 5 weeks per standing dosing recommendations (see [Section 5.3.1](#) for ibrutinib and venetoclax dosing).

Subjects who are unable to complete at least 12 cycles of combination therapy will not be eligible for Randomization but will continue to follow the same visit schedule until disease

progression. After disease progression subjects will enter the Post-PD Follow up Phase (Section 8.8).

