8.4. Reintroduction of Study Drug (MRD and FD Cohorts)

Subjects in the MRD cohort who are randomized and subjects in the Fixed Duration cohort who complete the fixed duration treatment may have study drug reintroduced if they become MRD positive (MRD cohort) or have confirmed progressive disease (either cohort). See [Section 5.4.2.2](#), and [Section 7.1.1.10](#) for TLS risk assessment and prophylaxis, respectively

Imaging for restaging is required prior to reintroduction. Medical Monitor approval is required prior to reintroduction of any study drug.

Creatinine clearance, Coagulation panel (PT/INR, aPTT) (for ibrutinib reintroduction), IGHV, karyotype, FISH, and ██████████ will be assessed at the first reintroduction visit. Prior to reintroduction, ECG and Echo/MUGA will be obtained, and cardiology consultation prior to reintroduction should be considered for patients with cardiac comorbid conditions or significant cardiac risk factors. The following procedures will be performed prior to reintroduction, and every 4 months for the first year, then every 6 months until PD, unless otherwise indicated.

- Physical exam
- Vital signs and Weight

- ECOG
- Hematology
- Serum chemistry
- CT/MRI (refer to [Appendix D](#) and [Appendix E](#) for specific timepoints)
- Overall response assessment Adverse events
- Concomitant medications
- Study drug compliance review
- Bone Marrow assessment (only at visit if needed to confirm CR, or if clinically indicated to confirm PD)
- ██████████ Assay ██████████
- ECG (prior to reintroduction then as clinically indicated)
- Echocardiogram or MUGA scan (prior to reintroduction to allow sufficient time for subsequent evaluation and clinical decision making, and then as clinically indicated)

Subjects will follow the schedule for their retreatment as outlined in [Appendix C](#), [Appendix D](#), and [Appendix E](#). Retreatment with ibrutinib or venetoclax or combination can be continued for the duration indicated, until disease progression as determined by investigator or until they meet criteria for withdrawal in [Section 9.2](#). Subjects must meet all of the criteria for reintroduction listed below. Per investigator discretion and in communication with medical monitor, initiation of reintroduction can be delayed until indication for treatment per IWCLL criteria is present.

Criteria for Reintroduction of Study Drug

Inclusions

1. ECOG Performance Status ≤ 2

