Appendix D. Schedule of Assessments for Reintroduction of Venetoclax (MRD Cohort only)

Study Visits	1 st month					2 nd month	Every 4 months for the first year, then every 6 months until PD (Day 1 of each visit)	Suspected PD (as soon as possible after suspected PD)	End-of-Treatment 30 Days °	Post PD Follow-up (Every 4 months)
	Week 1		Weeks 1-2		Wks 3-4	Wks 1 & 3				
	D-3 or D-2	D-1	D1 ^a	D2		D1				
Study Visit Windows	± 3 days (minimum of 7 days at each dose level of venetoclax)						± 3 days	Anytime	± 3 days	±14 d
Study Drug Administration and Dispensation										
Venetoclax	venetoclax: dose ramp up ^b					venetoclax: 400 mg PO daily ^b up to 24 cycles				
Procedures										
Medical Monitor Approval	Obtained before 1 st dose									
Concomitant medications			X		X	X	X	X	X	
Adverse events ^c			X	X	X	X	X	X	X	
Study drug compliance review ^d			X		X	X	X	X	X	
Physical exam, vital signs, weight, ECOG ^{ee}			X		X	X	X	X	X	
Overall response assessment	X ^f		X				X	X		
CT/MRI scan ^f	X						X (at the end of 4 months, at the end of 12 months, and annually thereafter)	X		
Bone marrow biopsy/aspirate for response (local lab and ██████████ central lab)							X (only if suspected CR / to confirm CR)	X (if clinically indicated)		
Tumor Lysis Syndrome (TLS) Risk Assessment ^h	X		X		X	X WK 1				
Tumor Lysis Syndrome Prophylaxis ⁱ	X	X	X	X	X	X WK 1				
Hematology (local lab) ^j	X		X	X	X	X WK 1	X	X	X	
Serum chemistry (local lab) ^j	X		X	X	X	X	X	X	X	
Creatinine clearance (eg, Cockcroft-Gault) (local lab)			X		X	X				
FISH (local or central lab) ^g	X									
Karyotype (central lab)	X									
IGHV (central lab) ^k	X									
Other Assessments										
12-lead ECG ^l	X						If clinically indicated			
ECHO or MUGA scan ^m	X						If clinically indicated			
Survival, including other malignancies										X
Any new anti-cancer therapy										X

Footnote:

- a. Day 1: To be collected pre-dose or within +/- 3 days, unless otherwise specified. FISH, Karyotype, IGHV, and ██████████ only on Week 1 D1
- b. Venetoclax: Day 1 dose of Cycle 4 Weeks 1-4, and Cycle 5 Week 1 should be administered at the investigational site. Subsequent daily doses may be self-administered at home.

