- c. Adverse Events: AEs are reported from the time the subject restarts study drug until 30 days following last dose of study drug. In addition to all routine AE reporting, all new malignant tumors including solid tumors, skin malignancies and hematologic malignancies are to be reported as adverse events.
- d. Study Drug Compliance: Includes subject instruction and routine review of study drug diary and evaluation of contents of study drug containers from home administration
- e. Physical Exam: Vital signs will be collected through end of treatment only. ECOG collected through disease progression.
- f. CT Scan: CT scans should be performed prior to reintroduction for restaging, at the end of 4 months, at the end of 12 months, and annually thereafter, and as clinically indicated. C4 CT Scan should be collected at C4D-3, while still allowing for appropriate TLS risk-guided interventions including hospitalizations if appropriate.
- g. Cytogenetics, FISH panel: Central lab if local FISH lab results are not available or if site cannot perform del17p and del11q testing.
- h. Tumor Lysis Syndrome Risk Assessment: Please see [Appendix H](#) for risk assessment categories. For baseline risk assessment, use Screening CT and C1D1 ALC.
- i. Tumor Lysis Syndrome Prophylaxis: Please see [Section 5.4.2.2](#) for TLS prophylaxis schedule, administration setting and frequency of serum chemistry monitoring assessments.
- j. Hematology and Serum Chemistry may be collected up to 24 hours prior to each ramp-up (Cycle 4 Weeks 1-4 and Cycle 5 Week 1), to allow for flexibility in start of ramp-up dose. Hematology and serum chemistry can be drawn on day of dosing to allow for comparisons, but results are not required before dosing decision is made. For subjects at high risk for TLS, additional hematology and serum chemistry samples will need to be collected 6-8 and 24 hours post-1st dose at Cycle 4 Weeks 3 and 4 and Cycle 5 Week 1 as part of TLS risk assessment. Please see [Table 4](#) for serum chemistry monitoring assessments.
- k. IGHV sample will be derived from one of the ██████████ samples collected
Karyotype: will be assessed from peripheral blood or bone marrow aspirate samples.
- l. ECG: 12-lead ECGs will be done *in triplicate* (≥1 minute apart) before reintroduction. In addition, ECG's may also be performed at the investigator's discretion, particularly in subjects with arrhythmic symptoms (eg, palpitations, lightheadedness) or new onset of dyspnea.

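### Appendix D footnote h, for TLS risk at venetoclax reintroduction, still names the first-course Screening CT and C1D1 lymphocyte count, visits that the schedule does not contain

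*Protocol*

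**What the plan says.** Appendix D is the schedule for reintroducing venetoclax in the MRD cohort. Footnote h belongs to its TLS Risk Assessment row. After referring the site to Appendix H for the categories, it says "For baseline risk assessment, use Screening CT and C1D1 ALC". Appendix A footnote q and Appendix B footnote n, which serve the first course of treatment, contain the same sentence.

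Other parts of the protocol bear on how to read it:

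- Section 8.2 sets the timing of all MRD-cohort visits from "Cycle 1 Day 1 (C1D1) as the anchor visit".
- Section 7.1.1.9 distinguishes two assessments: "At baseline and prior to initiating venetoclax in Cycle 4, all study subjects will be assessed for risk of developing TLS".
- Appendix D footnote f says "C4 CT Scan should be collected at C4D-3, while still allowing for appropriate TLS risk-guided interventions including hospitalizations if appropriate".
- Section 5.3.2.2 says "Standard TLS risk assessment, venetoclax dose ramp up, and TLS management should be employed at venetoclax reintroduction".
- Section 8.4 makes restaging imaging and Medical Monitor approval conditions of reintroduction. It refers sites to Sections 5.4.2.2 and 7.1.1.10 "for TLS risk assessment and prophylaxis, respectively".
- Appendix H defines the risk categories on tumor burden at Cycle 3.

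**The concern.** The TLS category decides how venetoclax is restarted. Under Table 4 and Section 5.4.2.2, high risk means hospital admission for the first 20 mg and 50 mg doses, intravenous as well as oral hydration, consideration of rasburicase if uric acid is raised, and closer chemistry monitoring. The category still matters at later doses: for high-risk subjects, Appendix D footnote j says that "additional hematology and serum chemistry samples will need to be collected 6-8 and 24 hours post-1st dose".

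A site that wants to know which scan and which lymphocyte count set the category will look at the footnote on that row. It is the only sentence in Appendix D that names both inputs, and it names two that belong to the first course. A site that followed it could err in either direction. It could admit a subject whose disease is now smaller, or treat as an outpatient a subject whose relapse is bulkier than the disease was at study entry.

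**Working it through.** No figure in the plan needs reproducing, so the main check sets the texts side by side.

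**1. Does the sentence have a visit to act on?** Appendix A has a Screening column and a Cycle 1 Day 1 column labelled as baseline, and it marks a TLS assessment at Cycle 1 Day 1. The sentence has a clear referent there. Appendix D begins at Week 1 D-3/D-2 of the first retreatment month. It marks TLS assessments at D-3/D-2, at D1, in Weeks 3-4 and in Week 1 of the second month. It has no Screening column, Cycle 1 column or baseline TLS assessment.

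**2. Could C1D1 mean the first day of retreatment?** Not in Appendix D. Its footnote b keeps the first-course labels for the ramp-up: "Day 1 dose of Cycle 4 Weeks 1-4, and Cycle 5 Week 1 should be administered at the investigational site". Section 8.2 reserves C1D1 for the anchor visit, and there would still be no Screening CT.

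**3. Could baseline mean study entry?** Section 7.1.1.9 treats the baseline assessment as separate from the one before venetoclax, and Appendix D schedules only the second kind. On this reading the sentence has nothing to govern. So it either supplies out-of-date inputs or is inert, and both are wrong in a reintroduction schedule.

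**4. What does the rest of the protocol supply?** Section 3.1.2 requires a restaging CT unless one was done within about 6 weeks. Appendix D places a CT, hematology and a TLS assessment together at D-3/D-2. Section 5.4.2.2 requires tumor burden to be assessed in every subject before venetoclax and leaves hospitalization to the investigator's assessment of risk. Section 7.1.1.9 asks for continuing reassessment at the ramp-up visits. All of these point to current data.

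**5. Related wording.** Appendix H's reference to Cycle 3 is ambiguous at reintroduction. Because Appendix D calls its ramp-up Cycles 4 and 5, the D-3 scan could be read as the Cycle 3 scan. Appendix E footnote h, for the Fixed Duration cohort, carries the same sentence. That schedule does have a first-month Day 1 visit, with venetoclax starting in the fourth month, so its cycles can be read as renumbered within retreatment. Appendix E is therefore only ambiguous.

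**6. Context figures.** None of these measures the effect of footnote h.

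- Age of the C1D1 count at C17D1, the point after which reintroduction becomes possible: 16 cycles × 28 days = 448 days, and 448 / 365.25 = 1.23 years.
- How quickly categories can move: Section 1.4 reports high-risk subjects falling from 28% to 7% after 2-4 cycles of ibrutinib (2 × 28 = 56 to 4 × 28 = 112 days) in treatment-naive disease.
- Chemistry time points over the five ramp-up doses, from the Table 4 rows:
  - High risk: 2 doses × 5 (pre-dose, 4, 8, 12, 24 h) + 3 doses × 3 (pre-dose, 6-8, 24 h) = 19.
  - Low or medium risk: 2 × 3 (pre-dose, 6-8, 24 h) + 3 × 1 (pre-dose) = 9. If table note d adds the 6-8 h and 24 h samples at each later dose, the count is 2 × 3 + 3 × 3 = 15.
  - Medium-risk subjects with creatinine clearance below 80 mL/min may also be hospitalized and monitored as inpatients, so the counts of 9 and 15 do not describe all of them.

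**The case against.** The strongest reply is that the sentence limits itself to the baseline assessment. In Appendix A it governs only the Cycle 1 Day 1 entry on the TLS row and leaves the Cycle 4 and Cycle 5 entries alone. Appendix D schedules no baseline assessment, so the sentence instructs nobody. To be misled, a site would have to set aside a mandatory new scan, a new blood count, footnote f, Section 5.4.2.2 and the exchange with the Medical Monitor, and use data more than a year old.

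Most of this stands. It defeats the stronger inference that a reader might draw, that the protocol tells sites to classify relapsed subjects on tumor burden from before the first course, or to disregard the restaging CT. The documents do not support that.

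It does not make the sentence correct. A safety footnote that at best applies to nothing, and at worst names the wrong inputs, should not remain on the row it is meant to explain. The other passages do not fully repair it either: Appendix H and Section 5.4.2.3 tie the category to Cycle 3, and no sentence expressly names both the CT and the lymphocyte count to use at reintroduction.

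A second fair objection is that the figures above do not measure this defect. The 448 days is calendar arithmetic, the 28% to 7% shift is first-course debulking, and the chemistry counts describe differences between categories. That is accepted in full.

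**Conclusion.** Appendix D footnote h is wrong as written: it carries a first-course instruction into a schedule that contains neither of the visits it names. It is a minor patient-safety wording correction. The surrounding provisions show that current data are intended and make harm unlikely. The error itself is certain from the text; any consequence for a subject is not.

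The number of subjects who might be misclassified cannot be estimated, because the documents give no misclassification rate and none can be derived from them. It would be a mistake to infer one from the context figures. No endpoint, hypothesis test or sample size is affected. The rating assumes that sites follow the D-3/D-2 procedures in Appendix D and the restaging requirement in Sections 3.1.2 and 8.4.

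**What to change.** In Appendix D footnote h, replace the sentence with: *For TLS risk category at venetoclax reintroduction, use the pre-venetoclax CT (the D-3 scan per footnote f) and the most recent ALC before dosing, reassessed at each ramp-up visit; do not use first-course Screening or C1D1 values.*

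Naming the D-3 scan matters because Section 3.1.2 accepts a restaging CT about 6 weeks old. Asking for the most recent lymphocyte count, not one fixed at D-3/D-2, keeps the footnote consistent with the D1 and later assessments and with Section 7.1.1.9.

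Make the matching clarification in Appendix E footnote h, and add to Appendix H that at venetoclax reintroduction these values replace the Cycle 3 tumor burden.

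The cost is a few lines of footnote and appendix text in an amendment. No procedure is added, because the CT and hematology are already scheduled at D-3/D-2 and the TLS reassessments are already marked in the table.

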Safety Run-in Period will be instituted to evaluate safety and tolerability of the combination, and determination of the recommended doses. Additionally, venetoclax will be introduced after 3 cycles (1 cycle = 28 days) of single-agent ibrutinib lead-in, representing the period after the ibrutinib-induced lymphocytosis peak and where most treated subjects will have experienced significant reduction in lymphadenopathy. Utilizing the previously published calculations to determine TLS risk categories for venetoclax based on tumor burden ([Seymour 2014](#), [Appendix H](#) as noted in the [VENCLEXTA® \(venetoclax\) prescribing information](#), TLS risk at baseline and at first assessment were calculated utilizing CT scans after 4 cycles of ibrutinib from the RESONATE-2 ibrutinib treatment naïve Phase 3 CLL study (N=135) and after 2 cycles of ibrutinib in PCYC-1102 Phase 1b/2 treatment naïve cohorts (N=27). The percent of subjects at high or moderate-risk for tumor lysis syndrome (TLS) at baseline was reduced from 81% to 59% after 2-4 cycles of ibrutinib, and the percent of subjects at high-risk for TLS at baseline was reduced from 28% to 7% after 2-4 cycles of ibrutinib. Due to transient increase in ALC, a minority (5%) of patients increased from low to medium risk at first assessment, however no patients increased from low or medium to high risk. For patients with treatment-naïve CLL or SLL with CrCl <80 mL/min, 36% (25/69) with medium TLS risk at baseline were reduced to low risk by first assessment and 26% (10/30) with high TLS risk at baseline were reduced to low risk by first assessment, further reducing the overall percent of patients requiring hospitalization ([Wierda 2017](#)). Therefore, employing a 3-cycle ibrutinib lead-in and sequencing ibrutinib prior to venetoclax should provide tumor debulking and convert higher TLS risk subjects to lower TLS risk subjects.

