Medium	Any LN 5 cm to <10 cm OR ALC ≥25 x10 ⁹ /L	Oral (1.5-2 L) and consider additional intravenous	Allopurinol ^b	Outpatient 
 Pre-dose, 6 to 8 hours, 24 hours at first dose of 20 mg and 50 mg Pre-dose at subsequent ramp-up doses Consider hospitalization for subjects with CrCl <80mL/min at first dose of 20 mg and 50 mg; see below for monitoring in hospital
High	Any LN ≥10 cm OR ALC ≥25 x10 ⁹ /L AND any LN ≥5 cm	Oral (1.5-2 L) and intravenous (150-200 mL/hr as tolerated)	Allopurinol ^b ; consider rasburicase if baseline uric acid is elevated	In hospital at first dose of 20 mg and 50 mg 
 Pre-dose, 4, 8, 12 and 24 hours Outpatient at subsequent ramp-up doses 
 Pre-dose, 6 to 8, and 24 hours

ALC = absolute lymphocyte count; LN = lymph node

- Administer intravenous hydration for any patient who cannot tolerate oral hydration.
- Start allopurinol or xanthine oxidase inhibitor 2 to 3 days prior to initiation of venetoclax.
- Evaluate blood chemistries (potassium, uric acid, phosphorus, calcium, and creatinine); review in real time.
- For subjects at risk of TLS, monitor blood chemistries at 6 to 8 hours and at 24 hours at each subsequent ramp-up dose. A ±30-minute window is acceptable for the 4 and 8 hr chemistry assessments, a ±1 hr window is acceptable for the 12-hour chemistry assessments, and a ±2-hour window is acceptable for the 24-hour chemistry assessments.
- Hematology and Serum Chemistry may be collected up to 24 hours prior to each venetoclax ramp-up (Cycle 4 Weeks 2-4 and Cycle 5 Week 1), to allow for flexibility in start of ramp-up dose. Hematology and serum chemistry can be drawn on day of dosing to allow for comparisons, but results are not required before dosing decision is made

Hydration: Ensure adequate hydration prior to initiating therapy with venetoclax and throughout the ramp-up phase, especially the first day of each ramp-up dose. Administer intravenous (IV) fluids as indicated based on overall risk of TLS or for those who cannot maintain adequate oral hydration.

Anti-hyperuricemic agents: Administer uric acid reducing agents (eg, allopurinol).

Start 2-3 days prior to initiation of venetoclax; consider continuing through the ramp-up phase.

Laboratory Assessments:

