Assess subject-specific factors for level of risk of TLS and provide prophylactic hydration and anti-hyperuricemics to subjects prior to first dose of venetoclax to reduce risk of TLS. Venetoclax will be administered orally once daily (QD) beginning with a dose ramp-up period. As shown in [Figure 1](#), the initial venetoclax dose is 20 mg QD. After one week of treatment at 20 mg QD, the dose will be escalated to 50 mg QD followed by subsequent increases, each after one week, to 100 mg QD, 200 mg QD and the maximum dose of 400 mg QD. The 5-week ramp-up dosing schedule is designed to gradually reduce tumor burden (debulk) and decrease the risk of TLS. All study subjects will be categorized in Cycle 3 according to their risk for developing TLS. Their dose management including during the dose ramp-up period will be conducted in accordance with their risk for developing TLS (see [Section 5.4.2.5](#)) and may include dose delay and/or dose reduction as required for prophylaxis and management of TLS.

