8.2.1.7. Cycle 16 Day 1 Visit**Pre-Dose**

The following procedures will be performed on Day 1 (± 3 days) of Cycle 16:

- Adverse events
- Concomitant medications
- Study drug compliance review
- Physical exam
- Vital signs
- ECOG
- Hematology
- Serum chemistry
- CT/MRI
- Overall response assessment
- Bone marrow biopsy (unless collected prior for CR assessment, and confirmed MRD-negative in BM)
- MRD assessment (bone marrow aspirate and peripheral blood). Bone marrow aspirate can be drawn ± 14 days from C16D1.
- ██████████ assays

Post-Dose

- Dispense ibrutinib and venetoclax for offsite use and provide study drug compliance instructions

MRD Cohort: Randomization Phase

Refer to the Schedule of Assessments ([Appendix A](#)) for a complete list of procedures to be performed at each scheduled study visit.

At Cycle 17 (following 3 cycles of ibrutinib lead-in, completion of 12 cycles of ibrutinib + venetoclax combination treatment, plus 1 cycle to evaluate MRD status) or within 3 days before Cycle 17 Day 1 visit, subjects will be randomized based on their MRD status. Randomization will occur via Interactive Response Technology (IRT) or alternative system provided by the Sponsor.

MRD-neg subjects will be randomized to either **ibrutinib or placebo**, and therapy should be continued until MRD-positive relapse, disease progression, unacceptable treatment-related toxicity, or other reasons outlined in [Section 9.2](#).

Subjects not obtaining confirmed MRD-neg responses (considered MRD-pos) will be randomized to either **ibrutinib + venetoclax or ibrutinib alone**. Ibrutinib and/or venetoclax should be continued until disease progression, unacceptable treatment-related toxicity, or other reasons outlined in [Section 9.2](#).

Central labs for MRD assessment will be used to inform randomization strata, and re-introduction of therapy. Local labs will be used to guide all other dosing-related decisions. In the event of rising MRD assessments, or of clinically suspected disease progression, the subject should continue to receive study medication, at the discretion of the Investigator, until MRD-positive relapse or disease progression is confirmed respectively.

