Appendix H. TLS Risk Category

For the management of tumor lysis syndrome prophylaxis, subjects will be classified in 3 risk categories based on the risk for developing medically concerning TLS with venetoclax administration. The Cycle 3 tumor burden assessed by the nodal disease and absolute lymphocyte count will be used to define each category as described below:

	Low Risk	Medium Risk	High Risk	
Lymph Nodes	All measurable lymph nodes with the largest diameter <5 cm by radiographic assessment	Presence of any single measurable lymph node with the largest diameter ≥ 5 cm and <10 cm by radiologic assessment	A single measurable lymph node with the largest diameter ≥ 5 cm by radiologic assessment.	Any single measurable lymph node with the largest diameter ≥ 10 cm by radiologic assessment
	AND	OR	AND	
Absolute Lymphocyte Count	$< 25 \times 10^9/L$	$\geq 25 \times 10^9/L$	$\geq 25 \times 10^9/L$	

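### Reintroduction schedules (Protocol Appendices D and E, footnote h) carry over a first-course TLS baseline instruction that matches no visit in their grids; Appendix H and Section 5.4.2.3 also cite only Cycle 3 data

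*Protocol*

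**What the plan says.** Protocol Section 8.4 opens reintroduction to "Subjects in the MRD cohort who are randomized and subjects in the Fixed Duration cohort who complete the fixed duration treatment". It then makes the appendices operative: "Subjects will follow the schedule for their retreatment as outlined in" Appendices C, D and E. Appendix D covers venetoclax reintroduction in the MRD cohort. Appendix E covers ibrutinib plus venetoclax retreatment in the Fixed Duration cohort.

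In both, the TLS risk assessment row carries footnote h, which refers to Appendix H for the categories and adds "For baseline risk assessment, use Screening CT and C1D1 ALC". Appendix H states: "The Cycle 3 tumor burden assessed by the nodal disease and absolute lymphocyte count will be used to define each category". Section 5.4.2.3 states: "All study subjects will be categorized in Cycle 3 according to their risk for developing TLS".

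Three other Appendix D footnotes keep first-course visit names. Footnotes b and j place on-site ramp-up dosing and the extra high-risk samples in Cycles 4 and 5. Footnote f places a CT at C4D-3. The Appendix D grid has no such cycles: ramp-up runs through the 1st month and into Week 1 of the 2nd month.

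**The concern.** The TLS class sets the intensity of prophylaxis. In Table 4 the High row requires intravenous hydration and monitoring "In hospital at first dose of 20 mg and 50 mg"; the Low row is outpatient with oral hydration. Old data could misclassify in either direction. A subject who was low risk at screening and progresses with bulky nodes could be under-monitored. A subject who was high risk at screening and has a low-burden MRD relapse could be hospitalized without need.

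The class does move with time. In the two earlier ibrutinib studies cited in Section 1.4, "the percent of subjects at high-risk for TLS at baseline was reduced from 28% to 7% after 2-4 cycles of ibrutinib", a change of 28 - 7 = 21 percentage points. That figure describes first-line debulking. It shows that timing matters but does not estimate misclassification at reintroduction.

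**Working it through.** The plan gives no figure to reproduce. The check is mainly a comparison of texts, with some arithmetic to bound the consequence of a literal reading.

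**Step 1. Does footnote h match a visit?**

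| Schedule | Columns with a TLS risk mark | Is there a Screening/C1D1 TLS mark? |
|---|---|---|
| Appendix A (first course), footnote q, same sentence | C1D1; before and during Cycle 4; Cycle 5 Week 1 | Yes, C1D1, as Section 8.2.1.1 confirms |
| Appendix D, footnote h | 1st month D-3/D-2, D1 and ramp-up weeks; 2nd month Week 1 | No |
| Appendix E, footnote h | 4th month D-3/D-2, D1 and ramp-up weeks; 5th month Week 1 | No; the 1st month Day 1 column has no TLS mark |

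The sentence has a function in Appendix A and none in Appendices D and E.

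**Step 2. Does another text name the data for the class at reintroduction?** Appendix H and Section 5.4.2.3 name Cycle 3. Appendix D has no lead-in, so it has no Cycle 3 of its own. Appendix E repeats a three-month lead-in, so Cycle 3 could there be read as the third month of retreatment. Section 5.3.2.2 asks for standard TLS risk assessment at venetoclax reintroduction without naming the data. Section 3.1.2 requires a restaging CT and sets a new baseline for response after progression, but sets none for TLS. Table 4 gives thresholds with no visit attached.

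**Step 3. Age of the named data, if taken literally in the MRD cohort.** Cycles are 28 days. Randomization is at Cycle 17 "or within 3 days before Cycle 17 Day 1 visit, subjects will be randomized based on their MRD status".

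- C1D1 ALC: 16 × 28 = 448 days at C17D1; 448 - 3 = 445 with the window.
- Screening CT: allowed up to 6 weeks (42 days) before enrollment, so up to 448 + 42 = 490 days old at C17D1.
- Cycle 3 tumor burden: 448 - 3 × 28 = 364 days; 361 with the window.
- Current data already scheduled: restaging CT within about 6 weeks (42 days); D-3 hematology with its 3-day window, up to 3 + 3 = 6 days.

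The 445 and 361 days are approximate minimum ages, because relapse or progression must follow randomization.

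**Step 4. What a High-to-Low error would remove, from the Table 4 rows.** Post-dose chemistry time points:

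- High: 4 (4, 8, 12, 24 h) × 2 steps (20, 50 mg) + 2 (6-8, 24 h) × 3 steps (100, 200, 400 mg) = 8 + 6 = 14.
- Low: 2 (6-8, 24 h) × 2 steps (20, 50 mg) = 4.
- Difference: 14 - 4 = 10 time points, plus 2 hospital stays.

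Table 4 note d can add draws for subjects judged at risk, so 10 is the difference between the rows only.

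**Step 5. Illustration with assumed values under the Appendix H rules (ALC in 10⁹/L).** Screening node 4 cm and ALC 20 is Low; relapse node 6 cm and ALC 30 is High. In reverse, screening node 6 cm and ALC 60 is High; relapse node 2 cm and ALC 3 is Low.

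**Step 6. The stale labels in Appendix D footnotes b, f and j.** These touch five on-site doses, three extra sampling steps and one CT. The intended visits can be inferred, because Sections 8.2.1.3.2 and 8.2.1.3.4 tie dosing to milligrams and week, and the grid marks a CT at D-3/D-2.

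**The case against.** A reader might infer that footnote h orders sites to classify a returning subject from scans and counts more than a year old. The documents do not support that. Sections 5.2.2, 5.3.4 and 7.1.1.9 separate the baseline assessment from the one before venetoclax, and in Appendix A the same sentence governs only the C1D1 mark. With no baseline column in Appendix D or E, the sentence is better read as an orphan than as an instruction for the D-3/D-2 assessment.

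Much else points to current data. Appendix D schedules CT, hematology and TLS assessment together at D-3/D-2. Its footnote f, despite the C4D-3 label, links the CT before venetoclax to TLS-guided hospitalization. Section 7.1.1.9 requires tumor burden assessment before venetoclax and continuing reassessment at ramp-up visits. Section 5.4.2.2 bases hospitalization on the investigator's assessment and keys chemistry to dose. Section 8.4 requires restaging imaging and Medical Monitor approval. A site would have to set aside results it had just obtained.

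This stands as to harm, and it limits the figures in Steps 3 and 4 to a literal reading. It does not rescue the wording: a safety footnote that names data from visits absent from its own grid, and points to an appendix that defines the class by Cycle 3, should be corrected.

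**Conclusion.** The point holds as a minor drafting error in a safety instruction. The sentence in footnote h of Appendices D and E matches no TLS visit there. The texts that say which data define the class name only first-course data, most clearly for Appendix D, which has no lead-in.

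The residual risk is small, because the surrounding text directs sites to current data. The figures of about 445 days and 10 of 14 time points assume that a site follows the stale labels and ignores that text. The documents do not give the number of subjects who reintroduce venetoclax, so no expected count of errors can be stated.

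A reader might also infer a threat to the TLS risk reduction endpoint. There is none: Protocol Section 10.4.8 and SAP Table 2 compare baseline with the end of the initial ibrutinib lead-in, and the analysis period in SAP Section 4 stops at reintroduction.

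**What to change.** - **Appendices D and E, footnote h:** replace the sentence with *Use the CT obtained before the first reintroduced venetoclax dose and the most recent ALC, with ALC updated at each ramp-up assessment.* Naming only the D-3/D-2 ALC would, read literally, freeze it through ramp-up, contrary to Section 7.1.1.9.
- **Appendix H and Section 5.4.2.3:** after the Cycle 3 reference add *or, at reintroduction, the tumor burden before the first reintroduced venetoclax dose*.
- **Appendix D, footnotes b and j:** change the Cycle 4 and Cycle 5 labels to *1st month Weeks 1-4* (*Weeks 3 and 4* for the extra high-risk samples) and *2nd month Week 1*.
- **Appendix D, footnote f:** replace the C4D-3 label with a CT before the first reintroduced venetoclax dose.

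A clarification letter or the next amendment can carry this. It adds no visits, procedures or subjects, since the CT and hematology are already scheduled.
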